Risk for sexual victimization. Due to the ethical proscriptions against replicating sexual victimization in the lab, we will assess risk for victimization using the Risk Perception Survey (RPS; Messman-Moore & Brown, 2006). The RPS consists of vignettes depicting forced sexual intercourse. The vignettes include clear (sexual comments, male persistence) and ambiguous (alcohol consumption, physical isolation) risk factors. They contain chronological statements that become progressively riskier as the man increases his coercion. Respondents imagine themselves interacting with the man and the RPS yields a "leave" variable, which reflects the point at which the participant indicates she would leave. We expect impaired risk perception as indicated by higher "leave" values when women are intoxicated and objectified.

Objectification and Alcohol-Involved Sexual Assault: Critical Moderators (Aim 3).

To address Aim 3, participants in Study 1 and Study 2 will complete measures of key moderators online prior to coming to the lab. In Study 1 men will complete the 10-item Sexual Experiences Survey-Short Form Perpetration (SES-SFP; Koss et al., 2007). The SES-SFP assesses the frequency (0 to 3+) of unwanted sexual contact, coercion, attempted rape, and rape. Men will also complete the 10-item Other-Objectification Questionnaire (OOQ) in which

they will rank order the importance of 10 objectifying attributes (e.g., sex appeal) and humanizing, internal attributes to assess overall objectification of women (Noll & Fredrickson, 1998; Grabe et al., 2005; e.g., relative importance of sex appeal vs. well-being, internal states, attributes in women). The ranking for the human attributes is subtracted from the ranking of the objectifying attributes with higher numbers indicating greater objectification of women.

Women in Study 2 will complete the 10-item Self-Objectification Questionnaire (SOQ; Noll & Fredrickson, 1998) that uses the same items, response format, and scoring procedure as the OQ, except people are asked to rank the objectifying and human attributes in themselves to assess self-objectification. Sexual victimization will be assessed with the 10-item Sexual Experiences Survey-Short Form Victimization; SES-SFV; Koss et al., 2007), which assesses the frequency of unwanted sexual advances using the same format as the SES-SFP, but with items worded for victimization rather than perpetration.

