Cover Page

Type of Document: Statistical Analysis Plan

Official Title of the study: Integrating Alcohol Myopia and Objectification to Understand Sexual Assault

NCT number: Not yet assigned

Date of document: 5-10-19

Statistical Analysis Plan

All analyses for Study 1 and 2 will be conducted using Mplus v. 7.4 (Muthén & Muthén, 2015), except descriptive statistics and multivariate analysis of variance models to investigate participant differences between intoxication condition groups (i.e., alcohol, placebo control), as well as order effects and repeated measures effects for the Eye-Tracking Objectification Task and the Implicit Association Task, will be examined using SAS v. 9.4 (SAS Institute, 2014). Manipulation checks will be assessed prior to analyses and appropriate controls (e.g., key demographics such as sexual orientation, race/ethnicity) will be included in the models. Study 1 tests the hypotheses for Aim 1 that intoxication causes more aggression in men (H1a), more impaired attention and objectification (H1b), that impaired attention and objectification mediate the relation between alcohol and aggression (H1c). Hypothesis 1a will be tested by regressing the measures of sexual aggression on intoxication (alcohol vs. placebo control) groups. Hypothesis 1b will be tested by regressing the measures of impaired attention and objectification separately on intoxication condition. Hypothesis 1c will be tested by simultaneously regressing the impaired attention measures on intoxication condition, the objectification measures on the impaired attention measures and intoxication condition, and the aggression measure on the impaired attention, objectification, and intoxication condition measures. The mediated effect of intoxication condition on aggression through each measure of impaired attention and of objectification, as well as the overall mediated effect through all measures, will be estimated using the MODEL INDIRECT statement in Mplus. Mediation will be tested using the bias-corrected bootstrap test (1,000 samples, MacKinnon, 2008).

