sexual victimization history (women), as well as, sex-related alcohol expectancies and rape myth acceptance to emerge as significant moderators of the relation between objectification and assault. Specifically, we expect sexual objectification to predict sexual aggression perpetration in men and self-objectification to predict victimization risk in women, but these effects should be particularly pronounced for people with a history of sexual assault (perpetration in men, victimization in women), as well as for people who endorse more rape myths and those who hold higher sex-alcohol expectancies. All continuous variables (i.e., all variables except the dichotomous measure of aggression in Study 1) will be grand mean centered prior to creating the interaction terms to improve interpretability as recommended by Cohen, Cohen, West, and Aiken (2003). The process will then be repeated for the measures of objectification and the moderator variables. Given the correlations between the moderator variables, the two-way interactions will be examined individually first. All significant interactions will be added to the model simultaneously to examine whether moderation remains. Type I error inflation across models will be controlled for using the Scheffe correction and no effects that explain less than 1% of the total variance will be considered important, regardless of statistical significance.

Missing data. Because the proposed studies are lab experiments, large amounts of missing data are unexpected. Data missing due to equipment malfunctions are missing completely at random (MCAR) and data missing due to nonresponses from participants will be considered missing at random (MAR). The methods for dealing with MCAR and MAR data are full information maximum likelihood (FIML) and multiple imputation (Enders, 2010). By default, Mplus uses FIML, so FIML will be used here for all analyses. Also, bias analyses will be conducted to examine demographics of people who participated in our study compared to people who were recruited for the study, but did not meet the inclusion criteria or who did not agree to participate in our study.

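### In the single-outcome regressions for H1a/H1b and H2a/H2b, FIML adds nothing to complete-case analysis, and no stated analysis compares completers with participants lost after randomisation

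*SAP*

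**What the plan says.** The SAP's Missing data paragraph expects few gaps ("large amounts of missing data are unexpected"). It treats equipment failures as MCAR and participant non-response as MAR, and names FIML and multiple imputation as suitable methods. It then settles on one: "By default, Mplus uses FIML, so FIML will be used here for all analyses". It names no auxiliary variables and gives no dropout rate.

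For Study 1 the SAP says: "Hypothesis 1a will be tested by regressing the measures of sexual aggression on intoxication (alcohol vs. placebo control) groups". H1b is tested by "regressing the measures of impaired attention and objectification separately on intoxication condition". The Study 2 paragraph carries the same approach to H2a/H2b, with two factors and their interaction. Only the mediation hypotheses, H1c and H2c, are fitted as simultaneous equations. Controls such as demographics are to be included, but the list is left open.

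The bias analysis compares the demographics of participants with those of "people who were recruited for the study, but did not meet the inclusion criteria or who did not agree to participate in our study". Separately, the SAP's opening paragraph plans multivariate analyses of variance of participant differences between the alcohol and placebo groups.

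The Protocol's Critical Moderators (Aim 3) section says that "participants in Study 1 and Study 2 will complete measures of key moderators online prior to coming to the lab". These measures are assault history (SES), chronic objectification (OOQ for men, SOQ for women), sex-related alcohol expectancies (SRAES) and rape myth acceptance (RMAS).

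**The concern.** A reader of the Missing data paragraph would take FIML to be an active remedy in every analysis. In a single-outcome regression on fully observed predictors it is not, because it simply omits people without the outcome. The MAR assumption then means MAR given condition and the chosen controls, and nothing more.

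This matters because the arms differ in what participants go through. The Protocol's Alcohol administration section gives one arm a dose targeting a BAC of at least .08% and a 20-minute absorption period, and the other a placebo and 10 minutes. Loss that differs by arm and is related to traits is therefore plausible, although the documents report none. The SAP itself expects assault history, alcohol expectancies and rape myth acceptance to modify the path to the outcome. Those scores should exist even for someone who does not finish the session, yet they play no stated part in the H1a/H1b and H2a/H2b models. The bias analysis, as worded, concerns who entered the study and not who was lost from it. At stake is the accuracy of the main randomised contrasts.

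**Working it through.** The plan states no figure on this point, so there is none to reproduce. All dropout rates and dependence strengths below are assumptions.

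**1. FIML equals complete-case analysis here.** With outcome y and complete predictors x, the observed-data likelihood is the product of f(y|x) over people with y observed, times the integral of f(y|x) over y for each person with y missing. That integral is 1, so those people drop out. In one simulated data set (N = 150, 24 outcomes missing), maximising this likelihood and fitting the completers gave the same slope, -0.087750, and for a binary outcome the same log odds ratio, -0.33814. This assumes one outcome per model, complete controls and no auxiliary variables.

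**2. Loss that depends on arm alone does no harm.** With 5, 10 or 20% loss in the alcohol arm only, unrelated to anything else (N = 150, 4,000 replicates), bias was within simulation noise, at most 4% of the effect.

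**3. Loss driven by a pre-lab trait.** Let T be a standardised trait correlated ρ with the outcome. A share d of the alcohol arm is lost, with logit P(lost) = c + 1.5T and c set so that the average is d. Since E(T) = 0, E(T | observed) = -[d/(1-d)] × E(T | lost), and the bias in the arm difference is ρ times this. E(T | lost) comes from integrating the logistic over a normal T.

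| d | log-odds per SD | E(T given lost) | E(T given observed) | bias, ρ = .3 | bias, ρ = .5 |
|---|---|---|---|---|---|
| .05 | 1.5 | 1.23 | -.065 | -.019 | -.032 |
| .10 | 1.5 | 1.10 | -.122 | -.037 | -.061 |
| .20 | 1.5 | 0.91 | -.227 | -.068 | -.113 |
| .20 | 0.5 | 0.39 | -.096 | -.029 | -.048 |

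Simulations with no true effect agree: .02-.04, .03-.06 and .07-.11 SD for the strong driver, and .03-.05 SD at 20% for the weak one.

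**4. Type I error at 20% loss, strong driver.** At N = 150 the simulated standard deviation of the estimate is about .173.
- Bias .07: .07/.173 = 0.40, and Φ(-1.96 + 0.40) + Φ(-1.96 - 0.40) ≈ .060 + .009 = .069.
- Bias .11: .11/.173 = 0.64, giving ≈ .093 + .005 = .097.
- With 210 in two arms the standard deviation is .173 × √(150/210) = .146, and the same sums give .077 and .117.

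Simulation over both sizes gave about 7 to 11%. In this scenario the first term, rejection in the direction opposite to the hypothesis, makes up nearly all of the error.

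**5. Loss driven by an earlier lab measure.** Here earlier-measured attention drives later loss of the outcome (log-odds 1.0 per SD, loss in the alcohol arm only). The SAP's coefficients of .26 and .39 are converted to 0/1 coding as .26/.5 = .52 and .39/.5 = .78. The true total effects are .52 × .26 = .135 and .78 × .39 = .304. Complete-case bias at 5/10/20% loss is -10/-17/-32% and -6/-12/-21%. A joint FIML model that includes the mediator stays within about 1% of the truth.

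**6. Loss driven by the outcome itself.** Both methods fail. At 5/10/20% loss, complete-case bias is -34/-71/-134% (.26 case) and -16/-33/-62% (.39 case). Joint FIML gives -32/-67/-126% and -14/-29/-54%.

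**7. How the trait is used matters.** With trait-outcome slopes of .1 in placebo and .5 in alcohol, N = 150 and 20% loss, the bias is -.114 for complete cases, -.055 with the association pooled over arms, and -.001 with arm-specific associations. Pooling leaves .055/.114 = 48% of the bias.

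**The case against.** Several stronger readings are tempting, and the documents do not support them.

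- *FIML gives no protection at all.* This is wrong. The estimate is valid when loss depends on condition and included controls, and unequal loss rates alone do not bias it (step 2). In H1c/H2c, FIML does use partly observed cases.
- *The bias analysis is the only check.* The planned multivariate comparison of alcohol and placebo groups could hint at selective loss if run on pre-lab scores in the analysed sample. The SAP names neither the variables nor the sample, and the comparison does not set completers against those lost.
- *The pre-lab scores are never used.* They enter the Aim 3 models, to which FIML also applies. The gap concerns H1a/H1b and H2a/H2b, and even there the list of controls is open.
- *The bias would produce false support for the hypotheses.* If high-trait people leave the alcohol arm, the bias runs against the hypothesised increase. At N = 150 and 20% loss, false positives in the hypothesised direction fall from 2.5% to 0.6-1.0%. The opposite selection would reverse this.

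The strongest remaining objection is size. The documents describe no reasons for dropout and no follow-up visit, and the larger figures need both heavy loss and a strong driver. A bias of .11 SD between equal groups corresponds to .11²/4 = .003, or 0.3% of variance. This stands as a limit on how much the point matters. It does not alter the fact that the stated method does nothing beyond dropping cases in these models, when better use of data already collected is available.

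**Conclusion.** The point holds as a cheap improvement of unknown practical consequence. In the separate H1a/H1b and H2a/H2b regressions, FIML gives no protection beyond complete-case analysis, and no stated analysis compares completers with randomised participants who were lost. At about 5% loss, trait-driven bias is small. It becomes material only if selective loss approaches 20% with a strong driver. Loss related to earlier lab measures can matter more in relative terms (step 5).

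The conclusion assumes that H1b is fitted one outcome per model, as the SAP's wording suggests. If the objectification measures were modelled jointly, FIML could borrow across them. It also assumes that controls are complete and that decliners were never randomised, which is the natural reading but is not stated.

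**What to change.** For H1a/H1b and H2a/H2b, bring the pre-lab SES, OOQ or SOQ, SRAES and RMAS scores, and earlier lab measures where observed, into the missing-data model. Either use multiple imputation within condition, which the SAP already names as a suitable class of method, or use FIML auxiliary variables with arm-specific associations. Pooled auxiliary variables are adequate only if those associations are similar across arms (step 7).

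Extend the bias analysis to everyone randomised: compare completers with those lost after randomisation, by condition, on the same scores.

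The cost is SAP wording and a short extra analysis on data already planned. In a single-trait check at N = 150 and 20% loss, precision was essentially unchanged (SD .172-.175 against .172-.174). That check did not test imputation from several scores within Study 2's four cells of about 210/4 = 52, where some added imputation variability should be expected. Someone who leaves before the lab measures can be imputed only from the pre-lab scores. Loss driven by the unobserved outcome is not cured, and nothing changes if nobody is lost.

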Statistical power. A single mediator model with standardized coefficients of $a=b=.26$ (approximately halfway between a small and medium effect as defined by Cohen, 1988) and $ab=.0676$ requires 148 participants to have statistical power of .80 for the bias-corrected bootstrap test (Fritz & MacKinnon, 2007). The mediation models for Aims 1 and 2 have two mediators entered serially (i.e., attentional impairment and objectification), however, with multiple measures of objectification. When X is dichotomous and two mediators are entered serially, 150 participants provide approximately .82 power to find a standardized mediated effect between .05 and .10 using the bias-corrected bootstrap test (Taylor, MacKinnon, & Tein, 2008) – a standardized mediated effect made up of three medium effects ($a=b_1=b_2=.39$) is equal to .06. Using multiple objectification measures slightly decreases individual effects due to partialling, but this will not affect the power calculations because they are based on partial effects. Research has found that alcohol predicts 10% of the objectification variance, and alcohol and objectification together predict 22% of the sexual assault variance ([name], et al., 2014; see also Haikalis et al., 2015). These are medium and large effects, so sample sizes of 150 (Study 1) and 210 (Study 2) will provide adequate power to test Aims 1 and 2. The power analyses for Aim 3 are different because they involve moderation effects in the context of mediation, which Hayes (2013) terms a conditional process model. An issue with detecting moderator effects is the small amount of variance explained by an interaction relative to a main effect (McClelland & Judd, 1993). No work on power for conditional process models has been conducted, but using G*Power (Faul, Erdfelder, Lang, & Buchner, 2007) to conduct a sensitivity analysis found that a sample size of 150 (Study 1) would provide .80 power to detect a moderation effect of $f^2 = .053$ (slightly larger than a small effect of $f^2 = .02$, Cohen, 1988) when the moderation term, a main effect term (for the 2 alcohol intoxication conditions), and two additional predictors are included in the model. A second sensitivity analysis found that a sample size of 210 (Study 2) would provide .80 power to detect a moderation effect of $f^2 = .044$ when the moderation term being tested, two main effects terms (one for the 2 objectification conditions and one for the 2 alcohol conditions), two interaction terms (between the intoxication

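### The SAP says that using several objectification measures leaves mediation power unchanged; this does not hold for the measure-specific indirect effects, and the .82 cannot be traced to the paths printed beside it.

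*SAP*

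**What the plan says.** The SAP's Statistical power section starts from a single-mediator benchmark with a=b=.26, which "requires 148 participants to have statistical power of .80 for the bias-corrected bootstrap test". It then moves to the serial model with a two-level X and one measure for each of the two mediators, and claims that "150 participants provide approximately .82 power to find a standardized mediated effect between .05 and .10 using the bias-corrected bootstrap test". The illustration beside this is that "a standardized mediated effect made up of three medium effects ($a=b_1=b_2=.39$) is equal to .06".

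The next sentence concedes that several objectification measures slightly reduce each individual effect through partialling, but adds that "this will not affect the power calculations because they are based on partial effects". As support, the SAP cites earlier results: alcohol explains 10% of the objectification variance, and "alcohol and objectification together predict 22% of the sexual assault variance". It concludes that 150 and 210 participants are adequate for Aims 1 and 2.

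The analysis text for Hypothesis 1c regresses "the aggression measure on the impaired attention, objectification, and intoxication condition measures" in one model, and Hypothesis 2c follows the same pattern. It promises the indirect effect through each measure and also the total through all of them. The protocol lists three objectification measures for men (eye tracking, brief implicit association task, questionnaire) and three self-objectification measures for women. Study 1's outcome, the choice of clip, is dichotomous.

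**The concern.** The .82 describes a chain with one attention measure and one objectification measure. The model to be fitted has three objectification measures side by side, each adjusted for the other two. If the measures are correlated, each partial path to the outcome is smaller than the path for one measure alone, and its standard error is larger. The SAP's clause is true only if the effect sizes it assumes are already the partial effects in the three-measure model. It does not show this, and .39 for each of three measures sits badly with the 22% it cites.

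At stake is how measure-specific null results in H1c and H2c are read. Someone relying on the stated power would treat a null path through gaze, implicit association or questionnaire as a null from a test with about 82% power, and so as evidence against that mechanism.

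**Working it through.** **Inputs from the documents.** N=150 and 210; stated power .82; paths .39; 10% and 22% of variance; three measures entered together; bias-corrected bootstrap; dichotomous outcome in Study 1.

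**Inputs assumed.** Two-sided .05; equal allocation; no missing data; inter-measure correlation r, which the documents do not give; 30% choosing the sexual clip; a linear model for the dichotomous outcome.

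**1. The plan's own figures.** The product is .39 × .39 × .39 = .0593, so the printed .06 is right. The single-mediator benchmark reproduces at about .81 with unit residual variances (.85 fully standardized), against the stated .80. For the serial model with one measure per mediator at N=150:

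- Fully standardized paths of .39: power about .99 or higher.
- X coded 0/1 with unit residuals: about .72 to .77 at a product of .06, about .82 near .085, and about .86 at .10.

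Neither scaling gives .82 at the printed paths. The SAP does not say how path a is scaled.

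**2. Can .39 be the partial path for each of three measures?** For three standardized measures with equal partial paths b and common correlation r, ignoring direct paths, R² = b²(3 + 6r). With b=.39, b²=.1521:

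| r | R² needed |
|---|---|
| 0 | .1521 × 3.0 = .456 |
| .3 | .1521 × 4.8 = .730 |
| .5 | .1521 × 6.0 = .913 |
| .7 | .1521 × 7.2 = 1.095 (impossible) |

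The smallest value for non-negatively correlated measures, .456, is about twice the cited .22.

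**3. Partial path if the three measures share an R² of .22 (assumption).** b = √(.22/(3 + 6r)), and the variance inflation factor is (1 + r)/((1 − r)(1 + 2r)):

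| r | b | VIF |
|---|---|---|
| .3 | .214 | 1.16 |
| .5 | .191 | 1.50 |
| .7 | .175 | 2.36 |

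**4. Power per specific indirect effect.** This is a bias-corrected bootstrap simulation of alcohol → attention → three measures → outcome. The alcohol-to-attention and attention-to-measure paths are .39, the total alcohol-to-measure effect is √.10 = .316, and b is taken from step 3.

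| Setting | r=.3 | r=.5 | r=.7 |
|---|---|---|---|
| N=150, continuous outcome | .77 | .63 | .42 |
| N=150, dichotomous outcome | .54 | .42 | .26 |
| N=210, continuous outcome | .87 | .72 | .51 |

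Repeat runs agree to within about .04. The N=210 row does not include Study 2's alcohol-by-objectification interaction.

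**5. Overall indirect effect.** In the same set-up, power for the sum over the three measures is about .99 or higher with a continuous outcome and about .93 to .96 with the dichotomous one. Under 0/1 coding with .39 paths and no 22% constraint, it is about .73 to .76 at N=150 for residual correlations of .3 to .5. That is close to the one-measure value on the same scaling.

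**The case against.** **The clause is conditionally true.** If the partial correlation really is held fixed, two more measures cost almost nothing. With power = Φ(atanh(ρ)√(N − 3 − k) − 1.96), where ρ is the partial correlation and k the number of covariates, going from k=2 to k=4 at N=150 moves the last path from .9986 to .9985 at ρ=.39, and from .893 to .889 at ρ=.26. This stands as algebra. It does not rescue the clause, because the SAP derives no partial effect for the three-measure model and the same sentence says the effects shrink.

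**The 22% is not a ceiling.** It is an earlier result, the number of measures behind it is not stated, and it leaves out attention. This stands. The figures in step 4 therefore rest on an assumption and do not prove what power the trial has. The 22% is, however, the only figure for explained outcome variance that the SAP offers.

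**The measures differ in kind**, so correlations of .5 to .7 may be too high. This stands in part. At r=.3 with a continuous outcome the gap from .82 is small at N=150, and at N=210 power exceeds .82. With independent residuals and a shared 22%, a closely related set-up gives about .88. But the step 4 paths alone imply some correlation. The direct alcohol path is .316 − .39 × .39 = .164, so even with independent residuals the measures correlate .39² + .164² + 2 × .39 × .39 × .164 ≈ .23.

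**Stronger inferences that the documents do not support.**

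- A reader might infer that .82 really belongs to paths of about .26 (product .018), outside the stated range. That holds only under full standardization. With X coded 0/1 and unit residuals, products of .05 to .10 give about .68 to .86, so .82 falls inside the SAP's range.
- A reader might take the untraceable .82 as proof that the partialling clause is wrong. The two points are separate. On the fully standardized reading, .82 even understates power at .39.

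**Conclusion.** Wrong as written, for the measure-specific indirect effects only. The SAP carries a one-measure power figure over to a model with three parallel measures and says nothing is lost. With .22 of outcome variance shared among the three, power per specific effect at N=150 is about .77 to .42 for a continuous outcome and .54 to .26 for the dichotomous one, over correlations of .3 to .7. At N=210 with a continuous outcome it is about .87 to .51. These sizes depend on the assumed correlations, the .22, the 30% event rate and the linear model. The shortfall is clear for Study 1's dichotomous outcome at every correlation shown. For a continuous outcome it is clear only from about r=.5.

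A reader might infer that the mediation hypotheses as a whole are underpowered. That is not supported: the overall indirect effect keeps power above .9 in the same set-up.

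Separately, the .82 is untraceable rather than shown to be false, because the scaling of path a and the point in the .05 to .10 range to which it refers are not given.

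**What to change.** - Delete the clause "this will not affect the power calculations because they are based on partial effects".
- State how path a is scaled and which partial effects lie behind the .82. Until that is settled, do not write a new pairing of effect and power for the one-measure model, since the answer changes with the scaling.
- Restate power for H1c and H2c separately for the overall and the measure-specific indirect effects. Use a simulation of the model to be fitted: three parallel measures, a dichotomous outcome in Study 1, and the alcohol-by-objectification interaction in Study 2. Show results over inter-measure correlations of 0 to .7.

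The cost is a wording change and one simulation. No participants are added and the design does not change. The drawback is that the stated power for the specific effects will look less favourable.

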Since the majority of the moderation hypotheses for Aim 3 involve manifest, continuous variables, moderation will be tested using the conditional process model framework (Hayes, 2013) rather than multi-group structural equation methods. The conditional process model framework involves taking the mediation models from Aims 1 and 2, and adding the two-way interactions between measures of myopia (impaired attentional capacity and sexual and self-objectification) and the moderators. We hypothesize, (a) prior objectification of women by men and (b) self-objectification in women to moderate the relation between impaired attention and situational sexual and self-objectification. Specifically, we expect impaired attention to predict sexual objectification in men, but these effects should be particularly pronounced for men who chronically objectify women. Likewise, we expect impaired attention to predict self-objectification in women, but that these effects should be particularly pronounced for women who chronically self-objectify. We also expect histories of sexual assault perpetration (men), or

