
and objectification factors), and two additional predictors are included in the model. This is equivalent to testing moderation of the relation between objectification and aggression/victimization risk in the mediation models, so sample sizes of 150 (Study 1) and 210 (Study 2) will allow adequate power to test Aim 3 (Figure 3).

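### The Study 2 sensitivity figure for Aim 3 should be f² = .038, not .044, and neither study's Aim 3 figure allows for the Scheffe correction that the SAP requires

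*SAP*

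**What the plan says.** The Statistical power paragraph of the SAP bases Aim 3 on two G*Power sensitivity analyses.

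- **Study 1:** "a sample size of 150 (Study 1) would provide .80 power to detect a moderation effect of $f^2 = .053", with four predictors: the moderation term, one main effect and two others.
- **Study 2:** "a sample size of 210 (Study 2) would provide .80 power to detect a moderation effect of $f^2 = .044", with seven predictors as listed: the moderation term, two main effects, "two interaction terms (between the intoxication" and objectification factors), and two others.

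The paragraph ends by saying that the two sample sizes "will allow adequate power to test Aim 3". It states no alpha and mentions no multiplicity adjustment.

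The SAP's text on Aim 3 moderation, which comes earlier, says that "Type I error inflation across models will be controlled for using the Scheffe correction". On what is tested, it describes "adding the two-way interactions between measures of myopia" and the moderators. It then names narrower hypotheses: chronic objectification acting on the path from attention to objectification, and assault history, alcohol expectancies and rape myth acceptance acting on the path from objectification to outcome. It adds that "The process will then be repeated for the measures of objectification and the moderator variables". Interactions are examined one at a time, and the significant ones are then entered together. No list of the tests covered by the correction is given, and no degrees of freedom for it.

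**The concern.** The two f² values are the only numbers behind the claim that Aim 3 is adequately powered. Two things looked wrong.

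First, the Study 2 value did not appear to follow from its own inputs. For a single-coefficient test the detectable f² is close to inversely proportional to N. Scaling Study 1's figure gives .053 × 150 / 210 = .038, not .044. In addition, two factors with two levels each have one interaction term, not two.

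Second, if both figures describe an unadjusted test while the plan commits to a Scheffe threshold, the stated .80 power does not belong to the planned test. A null moderation result could then be read as evidence against moderation when the study had little chance of detecting the effect size quoted. With the family undefined, two analysts could also apply different critical values to the same data.

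**Working it through.** **Inputs.** From the Statistical power paragraph: N = 150 with p = 4 predictors and f² = .053; N = 210 with p = 7 and f² = .044 (p = 6 if the 2×2 interaction is counted once); power .80; one tested term. Alpha is not stated. I assume .05, which step 1 supports.

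**Formula.** For one coefficient in a linear regression, the F test has 1 and v = N − p − 1 degrees of freedom and noncentrality λ = f² × N. Power is the probability that the noncentral F exceeds the critical value. The detectable f² is the value at which this probability is .80.

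**Step 1: reproduce Study 1.** v = 150 − 4 − 1 = 145. Solving at alpha .05 gives f² = .0530. With λ = .053 × 150 = 7.95, power is .800. The stated figure reproduces, which fixes the method and shows that the threshold was an unadjusted .05.

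**Step 2: apply the same method to Study 2.** v = 210 − 7 − 1 = 202. Solving gives f² = .0377. With p = 6 (v = 203) it is again .0377, so the extra interaction term makes no difference. With λ = .044 × 210 = 9.24, power is .857. Power of .80 at f² = .044 needs N = 181.

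Other settings do not recover .044 at N = 210:

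| Variant | Detectable f² |
|---|---|
| Two tested terms | .0466 |
| Alpha .025 | .0458 |
| Alpha .10 | .030 |
| Power .85 | .0432 |
| λ = f² × v | .039 |

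**Step 3: apply a Scheffe threshold.** For a family of k tests the 1-df statistic is compared with k × F(.95; k, v); k = 1 is the uncorrected test. The SAP does not give k, so every row with k of 2 or more is an assumption.

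| k | Critical F, S1 / S2 | Detectable f² at .80, S1 / S2 | Power at stated f², S1 (.053) / S2 (.044) |
|---|---|---|---|
| 1 | unadjusted | .053 / .038 | .80 / .86 |
| 2 | 6.12 / 6.08 | .073 / .052 | .64 / .72 |
| 3 | 8.00 / 7.95 | .090 / .064 | .50 / .59 |
| 4 | 9.74 / 9.67 | .105 / .075 | .39 / .47 |
| 9 | 17.50 / 17.34 | .170 / .120 | .09 / .14 |
| 12 | 21.83 / 21.60 | .204 / .144 | .04 / .06 |

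The last two rows show how far readings of the SAP can diverge. Three objectification measures by three moderators of the path to the outcome give 3 × 3 = 9. Adding attention by chronic objectification on three measures gives 9 + 3 = 12.

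**Step 4: do the stated figures already include a correction?** Study 1's .053 is the k = 1 value. Study 2's .044 lies below the k = 2 value of .052. Neither can include a Scheffe allowance for two or more tests.

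**The case against.** The .044 error is harmless on its own, because 210 women give more power than claimed. That stands, and this half of the point alone would be minor.

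The stronger objection is that the Scheffe figures rest on choices the SAP does not make. It does not say whether the correction applies to the one-at-a-time interactions or to the later joint model. The models are fitted in Mplus with full information maximum likelihood, so borrowing the error degrees of freedom of one linear regression is a simplification. The outcome in Study 1 is "the dichotomous measure of aggression in Study 1", so a linear-regression power figure is not the power of the planned aggression model. The SAP also does name its moderators and paths, so the family is not wholly open.

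Most of this stands as a limit on precision. The table is an illustration, the Study 1 column inherits the SAP's own approximation, and the k = 9 and k = 12 rows depend most on interpretation. It does not remove the conclusion. The separately fitted interaction models are the natural meaning of a correction across models, so an unadjusted first step is a strained reading. For any family of two or more the threshold is stricter than the one used. Naming four moderators per study does not settle the family either, because the SAP leaves open how they cross with the several objectification measures and whether the broader set of interactions belongs to it.

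**Conclusion.** The concern holds. At the alpha implied by Study 1, the Study 2 figure is wrong as written: .038 rather than .044 at .80 power, or .86 power at .044. That error is on the safe side.

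The adequacy statement is not supported for the test the SAP commits to. Under a Scheffe correction over as few as two tests, Study 2's margin is gone (.052 against the stated .044) and Study 1 needs .073 rather than .053. Larger families widen the gap.

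This rests on alpha .05, one tested coefficient, the SAP's linear-regression approximation and an assumed k. The direction does not depend on which k of two or more is chosen; the size does. It should be fixed, because it concerns stated power figures and an incomplete multiplicity rule.

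**What to change.** 1. Restate Study 2's uncorrected sensitivity as f² = .038 at N = 210, or report power of .86 at .044. List one intoxication-by-objectification term, or say what the second interaction term is meant to be.
2. For each study, list the hypothesised Aim 3 interactions that form the multiplicity family. Say whether the broader set of interactions belongs to it, which testing step the correction applies to, and what degrees of freedom the Scheffe threshold uses.
3. Rerun both sensitivity analyses at that threshold and report the detectable f² for each study, noting that Study 1's figure is a linear approximation for a dichotomous outcome.
4. Replace the unqualified claim of adequate power for Aim 3 with one that refers to the corrected figures.

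The cost is SAP wording and a short rerun. The uncorrected Study 2 figure improves, while for any family of two or more the corrected detectable effects in both studies will be larger than those now stated. No additional participants are needed.
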